### Other treatments

Patients will be expected to discontinue all prior treatments so as to effectively measure the sole effect of stenting.

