## **INVESTIGATIONAL PLAN**

### **HYPOTHESIS AND OBJECTIVES**

Papers published during the last seven years show that in patients with venous pulsatile tinnitus and significant venous sinus stenosis, tinnitus improves or resolves after stenting in the vast majority of patients. There have been 100 patients with venous sinus stenosis and venous pulsatile tinnitus reported in the literature (Table 1, attached document).

Fifty-four of these patients had Idiopathic Intracranial Hypertension and venous pulsatile tinnitus and the rest had isolated venous pulsatile tinnitus. After stenting, the venous pulsatile tinnitus resolved in 93/100, improved in 4/100 and remained unchanged in 3/100. This corroborates our experience at Cornell; out of 18 patients with venous sinus stenosis and venous pulsatile tinnitus treated by the PI with stenting, 17 had immediate resolution of the tinnitus. In one patient the tinnitus remained unchanged (anecdotal evidence; paper submitted for publication).

Our hypothesis is that venous pulsatile tinnitus is caused by the venous sinus stenosis and stenting would offer effective and long-term resolution of these symptoms. Our project aims to evaluate the long-term efficacy of venous sinus stenting in patients with severe intractable venous pulsatile tinnitus.

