#### **Primary Outcome:**

- The primary outcome will be complete or near-complete resolution of tinnitus at 12 months in more than 75% of treated patients.
- Primary Outcome Measure: No, slight, mild, or moderate tinnitus (grades 1, 2, and 3) on Tinnitus Handicap Inventory at 1, 6, 12, and 24 months

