**Reports on venous sinus stenting to treat pulsatile tinnitus in 100 patients (Table 1, attached document)**

Little has been published regarding endovascular treatment of pulsatile tinnitus due to venous stenosis in particular. We conducted a search of the literature available on PubMed detailing the outcomes of endovascular treatment of venous stenosis leading to pulsatile tinnitus and found that all were retrospective case reports or case series reports (Mathis et al. 1997, Donnet et al. 2008, Arac et al. 2009, Ahmed et al. 2011, Fields et al. 2013, Signorelli et al. 2011, Radvany et al. 2013, Baomin et al. 2014). From the search, 100 patients (Table 1) were found to have had endovascular treatment (stenting alone and stenting with angioplasty). Of those 100 patients, all but 3 patients reported resolved or improved tinnitus following the procedure. At follow-up of at least 2 months (ranging up to maximum 9 years), all treatments were considered successful with complete resolution of tinnitus except for 1 case which reported the return of tinnitus at a low level around 8 months (Mathis et al. 1997). All cases also reported long-term stent patency at follow-up. 8 patients experienced re-stenosis adjacent to the stent, 7 of which required re-stenting and 1 shunt placement. Only two cases experienced serious adverse events. One patient experienced vein perforation which eventually lead to a subdural hematoma. Another patient experienced subdural, subarachnoid and intracranial bleeding.

Baomin et al.'s (2014) paper was the most extensive report of endovascular treatment of pulsatile tinnitus due to venous stenosis. Forty-six cases were examined of patients who had failed medical treatment and masking therapies. Angioplasty and stenting were performed and all 46 patients reported immediate relief of tinnitus upon recovery from anesthesia. At 3-month follow-up, 2 patients reported recurrence of nonpulsatile tinnitus but this disappeared in both patients at the 6-month follow-up.

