### **Endpoints**

#### Primary Endpoints:

- Safety Endpoint: absence of procedure related and device related complications.
- Efficacy Endpoint:
  - o Improvement of more than one grade in the Tinnitus Handicap Inventory Questionnaire at 1, 6, 12, and 24 months after stent placement.

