**Patient Flow Chart**

**PRINT OUT OF ELECTRONIC CASE REPORT FORM**

Name: \_\_\_\_\_

Age: \_\_\_\_\_

DOB: \_\_\_\_\_

MRN: \_\_\_\_\_

Tinnitus Grade:  0  
 1  
 2  
 3  
 4  
 5Tinnitus Location:  Right  
 Left  
 BilateralVenous Dominance:  Right  
 Left  
 CodominantStenosis Location:  Right  
 Left  
 Bilateral

Stenting Date: \_\_\_\_\_

Stenting Result:  no residual stenosis  
 residual stenosis <50%  
 residual stenosis >50%  
 technical failure

Adverse Events:

- Serious
- Non-serious
- Unexpected

Description of Adverse Event

---

---

---

---

Tinnitus Grade:  0

Post-Stent (1 month)  1  
 2  
 3  
 4  
 5

Tinnitus Grade:  0

Post-Stent (6 mos)  1  
 2  
 3  
 4  
 5

Tinnitus Grade:  0

Post-Stent (12 mos)  1  
 2  
 3  
 4  
 5

Tinnitus Grade:  0

Post-Stent (24 mos)  1  
 2  
 3  
 4  
 5

MRV (12 mos)

- no residual stenosis or thrombosis
- in-stent stenosis <50%
- in-stent stenosis >50%
- new stenosis
- stent thrombosis

Any procedure-related adverse event after 24 months

---

---

---

---

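### The primary tinnitus endpoint has no rule for patients who receive a further intervention or tinnitus therapy, so as written their relief counts as a success of the study stent

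*Protocol*

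**What the plan says.** The Primary Outcome section sets the target: "The primary outcome will be complete or near-complete resolution of tinnitus at 12 months in more than 75% of treated patients". It gives the measure as "No, slight, mild, or moderate tinnitus (grades 1, 2, and 3) on Tinnitus Handicap Inventory at 1, 6, 12, and 24 months". The Endpoints section defines primary efficacy differently: "Improvement of more than one grade in the Tinnitus Handicap Inventory Questionnaire at 1, 6, 12, and 24 months after stent placement". The two definitions disagree on who responds (a fall from grade 4 to grade 3 meets the first and fails the second). They share one feature: each depends only on the grade at the visit.

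The section Other treatments states the intended effect: "Patients will be expected to discontinue all prior treatments so as to effectively measure the sole effect of stenting". It does not mention a second stent, a shunt or a new therapy, and it does not say how a patient who resumes an earlier therapy is scored.

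Data Analysis plans a simple proportion for each endpoint and reports all enrolled patients. The printed case report form has a grade box for each visit (for month 12, the one labelled "Post-Stent (12 mos)"), adverse-event categories with a free-text description, and a 12-month venogram result. It has no field for repeat intervention or for current tinnitus therapy.

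The protocol's literature review of 100 stented patients reports that "8 patients experienced re-stenosis adjacent to the stent, 7 of which required re-stenting and 1 shunt placement".

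**The concern.** The stated aim is the effect of the stent alone, but the endpoint measures the patient's state at the visit, whatever produced it. If the stent fails and something else brings relief before month 12, the patient is still a primary success. The resulting error has one direction, because scoring such a patient as a success can raise the proportion but never lower it. There is no control arm against which to see the inflation. With 20 patients, one or two cases can decide whether the target is met.

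The protocol's own benchmark shows the same practice. Although 8 of the 100 published patients were re-stented or shunted, the review says that at follow-up "all treatments were considered successful with complete resolution of tinnitus except for 1 case". If that statement covers all eight, at least seven re-treated patients were counted as successes.

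**Working it through.** The protocol gives no significance level, power or assumed response rate for its 20 patients, so there is no sample-size figure to reproduce. The calculation below shows only how large the effect could be.

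**Inputs**
- n = 20 (Number of Patients), taking all 20 as treated and assessed at month 12.
- Target: more than 75% (Primary Outcome).
- q, the share of patients who have a repeat intervention or use other tinnitus therapy by month 12. The protocol does not give it. I assume 2%, 4% and 8%; the last is the review's 8/100 taken at face value.

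**Step 1: the threshold.** 15/20 = 75% is not more than 75%; 16/20 = 80% is. At least 16 successes are needed, and each patient is 1/20 = 5 percentage points. One reclassified patient moves 15 to 16; two move 14 (70%) to 16 (80%).

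**Step 2: how many patients could be affected.** Under a binomial model, P(at least 1) = 1 − (1 − q)^20 and P(at least 2) = 1 − (1 − q)^20 − 20q(1 − q)^19.

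| Assumed q | Expected number, 20q | P(at least 1) | P(at least 2) |
|---|---|---|---|
| 2% | 0.4 | 1 − 0.668 = 0.33 | 1 − 0.668 − 0.272 = 0.06 |
| 4% | 0.8 | 1 − 0.442 = 0.56 | 1 − 0.442 − 0.368 = 0.19 |
| 8% | 1.6 | 1 − 0.189 = 0.81 | 1 − 0.189 − 0.328 = 0.48 |

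**Step 3: effect on meeting the target.** Suppose the success rate from the stent alone is exactly 75%, so that the target should not be credited. The exact binomial chance of 16 or more out of 20 is 0.41. If a further q of patients are relieved by other treatment and all are scored as successes, the chance is taken at 75% + q: 0.50 at 77%, 0.59 at 79% and 0.76 at 83%. This is the largest effect for each q, because it makes every affected patient a stent failure turned into a success.

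**Step 4: whether another section already settles the scoring.**
- Secondary Endpoints include no recurrence within 24 months and patency at 12 months. These are reported separately and leave the primary proportion as it is.
- Criteria for Early Termination allow removal for significant deviation or non-compliance. They do not name re-treatment and assign no outcome, while Data Analysis says all enrolled patients are reported.
- Documenting Adverse Experiences asks for the method used to treat each event. This helps to find repeat interventions but is not a scoring rule.

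None of these changes how the primary endpoint is counted.

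**The case against.** **The protocol is silent rather than wrong, and an analysis plan could supply the rule.** It is true that the protocol nowhere says the grade is taken regardless of other treatment; that follows from the absence of any condition. But the definitions, the stated aim and the form are all fixed in this document and do not fit together. A later plan also could not fully apply a rule on tinnitus therapy that the form does not record.

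**A reader might infer that affected patients could not be identified at analysis.** The documents do not support that for repeat interventions. A second procedure requiring admission meets the serious adverse event definition, every adverse experience must be recorded with onset date and treatment, and the form has free text and a venogram result. Such cases would probably surface, though not in a dedicated field. The gap is complete only for resumed or new tinnitus therapy.

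**A reader might take 8/100 as the rate of rescued failures to expect here.** It is not. It counts re-stenosis beside the stent, over follow-up from 2 months to 9 years, and the review does not say that tinnitus had returned in those patients. Fifty-four of the 100 had idiopathic intracranial hypertension, for which the protocol describes shunting as a treatment option, whereas this trial excludes visual field defects or papilledema consistent with raised intracranial pressure. The 81% and 48% are therefore upper-end figures.

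**Resumed therapy is a weak route to success.** This stands. Entry requires grade 4 or 5 despite at least 3 months of earlier treatment, so therapies that have already failed are unlikely to turn a stent failure into a response. A patient who resumes them might also be removed for non-compliance.

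**The target may be met comfortably anyway.** The review reports that "the venous pulsatile tinnitus resolved in 93/100, improved in 4/100 and remained unchanged in 3/100". At a true 93%, the chance of 15 or fewer out of 20 is 0.01; at 85% it is 0.17. The scoring rule matters for the decision mainly if the true rate is nearer the target. Visit-by-visit grades may also show a failure that preceded rescue.

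**Conclusion.** The point holds in a limited form. Both primary efficacy definitions rest on the visit grade alone, and this does not deliver the stent-only effect that the protocol says it wants to measure. Counting relief from other treatment as success can only push the proportion up, by 5 points per patient.

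The size is uncertain and probably modest: on assumed 12-month rates of 2% to 8%, between 0.4 and 1.6 patients of 20 are expected to be affected. These figures rest on independent patients and on all 20 being treated and assessed. For the endpoint itself to be inflated, the affected patients must also have been stent failures who then reached a responder grade. The documents do not show that this will happen often, or that the target would be met only because of it.

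**What to change.** - In both Primary Outcome and Primary Endpoints, state that a patient counts as a non-responder for the primary efficacy proportion if, before the visit, they have had a repeat venous sinus intervention, a shunt or other surgery for tinnitus, or if they are using resumed or new tinnitus therapy at the visit.
- Report the proportion based on the observed grade, whatever other treatment was received, alongside it.
- Add fields to the case report form at each visit: repeat intervention (type and date) and current tinnitus therapy (yes or no, and type).

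The cost is protocol wording and a few form fields at visits that already take place. The reported success rate may be slightly lower. The change affects only how outcomes are counted, and has no bearing on which treatment any patient receives.

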### **Endpoints**

#### Primary Endpoints:

- Safety Endpoint: absence of procedure related and device related complications.
- Efficacy Endpoint:
  - o Improvement of more than one grade in the Tinnitus Handicap Inventory Questionnaire at 1, 6, 12, and 24 months after stent placement.

#### Secondary Endpoints:

- No recurrence of tinnitus within 24 months after treatment
- Stent patency at 12 months after treatment
- Adverse events probably or possibly related to the treatment within a 24-month period after treatment

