#### **Secondary Outcomes:**

- Long-term success of treatment (clinical recurrence rates over 24 months)
- Long-term patency of the stent (stent patency 12 months after treatment)
- Rate and severity of adverse events probably or possibly related to the treatment within a 24-month period

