## **Our experience treating patients with Idiopathic Intracranial Hypertension and pulsatile tinnitus using venous sinus stenting**

Our institution has had success treating patients (N=20) who have idiopathic intracranial hypertension (IIH) concomitant with pulsatile tinnitus (N=18). In addition to pulsatile tinnitus, IIH patients have symptoms of headache, diplopia, visual field deficits, hearing loss, and vertigo. These patients typically undergo a regimen of medication as the first line of treatment. If the IIH becomes refractory to maximal medication, surgery (shunt placement) or stenting are options for treatment. Stenting of the dural venous sinus has been shown to eliminate tinnitus among pseudotumor cerebri patients (Mathis et al. 1997), and we were able to replicate this effect in our study. We enrolled patients in the FDA approved trial “Venous sinus stenting in patients with idiopathic intracranial hypertension refractory to medical therapy” over a three-year period from January 2012-December 2014. Patients eligible for venous stenting outside the trial were enrolled in a prospective database. Out of the 20 patients, 18 experienced pulsatile tinnitus. Nine patients presented with grade-4, 5 patients had grade-3, and 2 patients each had grade-2 and grade-1 tinnitus. Out of eighteen patients with IIH and pulsatile tinnitus treated with venous sinus stenting, there was immediate resolution of tinnitus in seventeen patients. All patients had unilateral distal transverse-sigmoid sinus stenting. There was no recurrence of tinnitus for the duration of follow-up period. The 1 patient who had persistent tinnitus after the procedure had grade-1 tinnitus and did not report any change in severity. No serious neurological adverse events occurred after the procedure. All non-serious adverse events were treated without the need for invasive treatment. Of these, seven patients experienced headaches afterwards and were treated with steroids, one patient developed a small retroperitoneal hematoma, and another patient developed free intra-abdominal hemorrhagic fluid collection a few days after the procedure that was attributed to a ruptured hemorrhagic ovarian cyst. There were no neurological adverse events or device related complications.

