### **Inclusion and Exclusion Criteria**

#### Inclusion criteria:

- Severe or catastrophic venous pulsatile tinnitus defined as Grades 4 or 5 on Tinnitus Handicap Inventory
- 50% or more stenosis of the lateral venous sinus on MRV or CTV, ipsilateral to the side of more severe tinnitus
- Length of stenosis  $\leq$  70mm
- Transstenotic gradient  $\geq$  4mm Hg evidenced by venous manometry
- Failure of conservative or non-surgical therapies (including sound therapy, sound masking, hearing aids, tinnitus retraining (desensitization) therapy. Failure is

defined as Grades 4 or 5 on the Tinnitus Handicap Inventory despite prior treatments that have lasted for at least 3 months.

- Adults, age > 18 years
- Informed consent signed by the patient

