**Follow-up (Patient Flow Chart, page 28)**

**Office visits**

Office visits with neurologic evaluation will be performed at one, six, twelve, and twenty-four months after treatment. At this time the patients will also fill the Tinnitus Handicap Inventory Questionnaire. The visits will last about 45 minutes.

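### The 24-month recurrence endpoint names neither type nor side of tinnitus, and the follow-up form records neither, so return of the venous sound on the stented side cannot be told from other tinnitus

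*Protocol*

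**What the plan says.** The aim, in Hypothesis and Objectives, is long-term resolution of tinnitus that is venous, pulsatile and caused by the stenosis. Entry follows that aim. The Inclusion criteria require severe venous pulsatile tinnitus and a stenosis "ipsilateral to the side of more severe tinnitus". The Exclusion criteria remove non-pulsatile tinnitus.

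Recurrence appears twice. Secondary Outcomes lists "Long-term success of treatment (clinical recurrence rates over 24 months"), and Secondary Endpoints lists "No recurrence of tinnitus within 24 months after treatment". Neither says which type of tinnitus counts, or in which ear.

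For follow-up, Office visits states: "Office visits with neurologic evaluation will be performed at one, six, twelve, and twenty-four months after treatment". It continues: "At this time the patients will also fill the Tinnitus Handicap Inventory Questionnaire". The printed case report form has a tinnitus location item (right, left or bilateral) once, among the baseline items before the stenting date. Its four follow-up blocks hold a tinnitus grade from 0 to 5 and no other tinnitus item. Pulsatility is not a field at any time point.

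The Protocol's review of earlier reports says of the largest series, 46 patients, that at 3 months "2 patients reported recurrence of nonpulsatile tinnitus but this disappeared in both patients at the 6-month follow-up".

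**The concern.** The trial selects patients by type and side of tinnitus and then stops recording both. The question behind the recurrence endpoint is whether the sound produced by the stented stenosis comes back. An overall handicap grade answers a different question: how much tinnitus of any kind, in either ear, troubles the patient.

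The two can differ in this trial. A patient may enter with tinnitus on both sides and receive a stent on one. A patient may also develop non-pulsatile tinnitus after the procedure, as happened in the series that the Protocol relies on most. In either case a high or rising grade could be read as failure of the stent when the venous sound on that side is gone. Because the information is not collected, no later definition or analysis plan can recover it.

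**Working it through.** The Protocol states no figure on this point, so there is nothing to reproduce. The check compares what is recorded before and after stenting, and then asks what the documents allow one to say about size.

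**1. Fields before and after stenting**

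| Item | Entry and baseline | Follow-up |
|---|---|---|
| Overall tinnitus grade | Recorded | Recorded at 1, 6, 12 and 24 months |
| Side of tinnitus | Recorded once (right, left, bilateral) | No field |
| Pulsatile or not | Decides eligibility; no form field | No field |

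The other follow-up items are a neurologic evaluation at each visit, one audiometric assessment at 3 months aimed at inner ear function, one venogram at 12 months, and adverse event recording. None is specified to record whether the sound is pulse-synchronous or on which side it is heard.

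**2. Can bilateral tinnitus be enrolled with a one-sided stent?** Yes.
- The inclusion wording about the more severe side presupposes that there may be a less severe one.
- The form offers a bilateral option.
- The Venous sinus stenting section places the stent on the dominant side or, with co-dominant sinuses and bilateral stenosis, on the side of worse tinnitus.

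**3. What the form cannot separate.** Take three patients with the same raised grade at 24 months:
- A: the pulse-synchronous sound has returned on the stented side.
- B: the stented side is silent, and tinnitus on the other side has worsened.
- C: the stented side is silent, and new non-pulsatile tinnitus has appeared.

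Only A is recurrence of the treated condition. All three have the same entry on the form, whatever change in grade is taken to mean recurrence.

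**4. Scale, for illustration only.** Inputs: 2 of 46 patients (the cited series) and 20 patients (Number of Patients).
- Rate: 2/46 = 4.3%; exact 95% interval 0.5% to 14.8%.
- Expected in 20 patients: 20 × 2/46 = 0.87; range 0.11 to 2.97 over that interval.
- Chance of at least one: 1 − (44/46)^20 = 0.59; range 0.10 to 0.96.
- Weight of one patient: 1/20 = 5 percentage points. For a recurrence proportion, 0/20 is 0% (exact 95% interval 0 to 16.8%), 1/20 is 5% (0.1 to 24.9%) and 2/20 is 10% (1.2 to 31.7%).

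**5. Does that rate predict misclassification here?** No. The two events were seen at 3 months and were gone at 6. The inventory is scheduled at months 1 and 6, with none between. On the cited time course these events would be absent at month 6, and nothing says they were present at month 1. The figures in step 4 show that the distinction is real and that one patient carries weight. They do not forecast a count.

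**6. The other-side route.** The Protocol gives neither the share of patients with bilateral tinnitus nor a rate of new or worsening tinnitus in the other ear, so this part has no number.

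**The case against.** Several points on the other side are fair.

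- **Recurrence ordinarily means return of the treated symptom.** The Protocol's aim identifies that symptom, and an unseen analysis plan may define the term. A definition would help, but it cannot be applied to data that hold no side or type.
- **Entry criteria limit the problem.** The stenosis must be on the worse side. Non-pulsatile tinnitus and otologic disorders are excluded, as is some contralateral tinnitus in bilateral stenosis. This reduces the problem at baseline. It does not exclude bilateral tinnitus as such, and it does not govern what appears later.
- **The 12-month venogram helps interpretation.** It records in-stent stenosis, new stenosis and thrombosis. It is one time point, however, and does not identify what the patient hears.
- **The gap is read partly from a printed form.** The Patient Flow Chart cited for follow-up is not visible in the text, and an investigator could use the adverse event free text. Nothing in the visible text requires this.
- **Severe handicap from the other ear is a legitimate failure on a handicap measure.** This stands for the primary outcome, which is one reason to leave that outcome alone.

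A reader might infer three stronger things that the documents do not support:

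- That the 2 of 46 patients would have counted as recurrences here. The visit schedule does not bear this out.
- That misclassification could tip the 75% target, since 16/20 (80%) exceeds 75% and 15/20 (75%) does not. That target is judged on the grade at 12 months. The cited events were gone by month 6, their severity is not reported, and a patient must be at grade 4 or 5 to fail. No link is shown, and the change proposed here would not alter that result.
- That a low grade has been shown to hide a persisting sound, because in the institution's own series "The 1 patient who had persistent tinnitus after the procedure had grade-1 tinnitus". That patient's severity did not change, the grading scale is not named there, and entry here requires grade 4 or 5. The case does not show what a fall from 4 or 5 to a low grade means.

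**Conclusion.** The point holds for the recurrence endpoint. As written and as recorded, that endpoint cannot separate return of pulse-synchronous tinnitus on the stented side from non-pulsatile or other-side tinnitus. Bilateral tinnitus with a one-sided stent is the clearest route to misclassification.

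The size is 5 percentage points of the recurrence proportion for each patient affected. The number affected is unknown. The conclusion assumes that the printed form is complete for tinnitus items and that no unseen document adds side or type at follow-up.

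This is a low-cost improvement to a secondary endpoint. It is not a threat to the primary result. It would also be too strong to say that recurrence can never be interpreted: a patient with one-sided pulsatile tinnitus, a later rise in grade and restenosis on the venogram would be fairly clear. The loss is in the patients for whom those facts do not line up.

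**What to change.** - **Record:** at baseline and at the existing visits at 1, 6, 12 and 24 months, for each ear, pulse-synchronous tinnitus (yes/no) and non-pulsatile tinnitus (yes/no). The printed form shows no item for the stented side, so add one.
- **Define:** in Secondary Outcomes and Secondary Endpoints, recurrence as return of pulse-synchronous tinnitus on the stented side. List new or persisting non-pulsatile and other-side tinnitus separately.
- **Keep:** the Tinnitus Handicap Inventory grade as the primary measure.

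The cost is two questions per ear, so four yes/no items at each of five time points, plus the wording of the form and the two endpoint sections. There are no new visits and no change in treatment. The downside is that the items are patient-reported and unvalidated. They should serve the secondary endpoint and interpretation only. The change has to be made before the visits take place, because answers not collected at a visit cannot be reliably recovered afterwards.
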